5.5.6 Rescue medication

Guidance on handling hyperkalemia, hypotension, and renal dysfunction are provided to investigators in Appendix 1, Appendix 2, Appendix 3, and Appendix 4 respectively. Patients may receive open-label ACEIs and/or ARBs during the study **ONLY** if the study medication has been discontinued either temporarily or permanently. A 36 hours washout phase of study drug is needed before start of an ACEI.

Use of rescue medication must be recorded on the Concomitant medications/Significant non-drug therapies Record in the CRF.

5.5.7 Concomitant treatment

The investigator should instruct the patient to notify the study site about any new medications he/she takes after the patient was enrolled into the study. All medications, procedures and significant non-drug therapies (including physical therapy and blood transfusions) administered after the patient was enrolled into the study must be recorded.

5.5.8 Other concomitant treatment

The investigator should instruct the patient to notify the study site staff of any changes in concomitant medications (new medications or changes in dose regimens of existing medications). All concomitant medications and significant non-drug therapies (including physical therapy and blood transfusions) administered after the patient starts treatment with the study medication must be listed on the Concomitant Medications/Significant Non-Drug Therapies eCRF.

ACEIs and ARBs

Patients' pre-study ACEIs/ARBs will be replaced by the study medications.

The concomitant use of open-label ACEIs or ARBs is strictly prohibited while the patient is receiving study medication. If the investigator believes that addition of an ACEI or ARB is necessary, then study drug must be discontinued. **Study medication should be stopped 36 hours prior to addition of open-label ACEI.** If not already treated with an aldosterone antagonist, consideration should be given to adding this therapy rather than an ACEI or ARB.

Similarly, if study medication is to be restarted, the open-label ACEI should be discontinued 36 hours prior to resuming study medication.

Heart failure medications and other cardiovascular medications

The patient should be on an optimal medical regimen of background HF medications which have to be stable 4 weeks prior to screening at Visit 1 and during the screening period until randomization at Visit 3. Background HF medication must include an individually optimized dose of a β -blocker (i.e., maximally tolerated dose) at a stable dose for at least 4 weeks prior to study entry, unless contraindicated or not tolerated. This also includes the use of ivabradine according to guideline recommendations. Use of an aldosterone antagonist should be considered in patients eligible for this study. In self-identified black patients, the use of isosorbide dinitrate/hydralazine hydrochloride (e.g., BiDil[®]) should be considered **with caution**.

Diuretics may be used and may be adjusted throughout the length of the study at the discretion of the investigator.

Every effort should be made to keep the dose level of these background disease-modifying HF medications stable throughout the entire study including screening period. However, if the patient's condition warrants a change in any of these medications (for example, if the investigator believes a disease-modifying medication is causing an adverse event), it is allowed at the discretion of the study investigator.

If a patient experiences any AEs that may be contributed to the study drug, other HF medication, or other CV medications, the investigator should adjust non-disease-modifying medications (e.g., CCBs, nitrates, α -blockers, and diuretics) first in an attempt to alleviate the AEs.

Medications known to raise potassium levels

Potassium-sparing diuretics, potassium supplements, aldosterone antagonists, and any other medications known to raise potassium levels should be used with caution while the patient is receiving the study medication due to the increased possibility of occurrence of hyperkalemia. The investigator is encouraged to assess patients' potassium levels regularly, especially in those who are receiving these medications.

Concomitant administration of renin inhibitors, such as aliskiren, is prohibited.

Phosphodiesterase-5 (PDE-5) inhibitors

PDE-5 inhibitors should be used with caution while the patient is receiving study medication due to the increased possibility of occurrence of hypotension.

Nesiritide and intravenous nitrates

Nesiritide and intravenous nitrates should only be used as the last choice as vasodilators are known to modulate VO_{2max} . The concomitant administration of LCZ696 with nesiritide and intravenous (i.v.) nitrates has not been studied. In the event a study patient requires the concomitant administration of nesiritide and/or i.v. nitrates with the study medications, the investigator should consider starting them at a lower dose or a slower infusion rate while monitoring the patient's blood pressure carefully.

Statins

Caution should be exercised upon co-administration of LCZ696 and statins such as atorvastatin, simvastatin, pravastatin, and/or pitavastatin. The co-administration of LCZ696 increased the C_{max} (maximum plasma concentration) of atorvastatin and its metabolites by 68% -108%, although the AUC was not significantly changed (<34%).

L-thyroxin

The patient should be on an optimal medical regimen of L-thyroxin medication in case of thyroidal dysfunction. This must include an individually optimized dose at a stable dose for at least 3 months prior to study entry. All changes administered after the patient starts treatment with the study medication must be listed on the Concomitant Medications/Significant Non-Drug Therapies eCRF.

Other medications

Bile acid sequestering agents, such as cholestyramine and colestipol, are prohibited to avoid interference with study drug absorption.

5.5.9 Prohibited Treatment

Use of the treatments displayed in Table 5-2 is NOT allowed after the start of investigational treatment. Treatment with an investigational drug other than study treatment is also prohibited.

Table 5-2 Prohibited treatment

Medication	Action to be taken
Any ACEI	Discontinue study drug. The open label ACEI must be stopped for ≥ 36 hours prior to re-initiation of study drug
Any ARB	Discontinue study drug. The open label ARB must be stopped prior to re-initiation of study drug and stop ARB
Renin inhibitors (confounding safety: increased likelihood of occurrence of hyperkalemia)	Discontinue study drug. The open label renin inhibitor must be stopped prior to re-initiation of study drug
bile acid sequestering agents (cholestyramine, colestipol; potential interference with study drug absorption)	none

5.5.10 Discontinuation of study treatment and premature patient withdrawal

The emergence of the following circumstances will require study drug discontinuation:

- Withdrawal of informed consent
- Pregnancy (see [Section 7.4](#) Pregnancy reporting)
- Investigator thinks that continuation would be detrimental to the patient's well-being
- Suspected occurrence of angioedema. A patient with any signs or symptoms of clinically significant angioedema should be thoroughly evaluated by the investigator and constitute a reason for temporary or permanent discontinuation of study treatment.
- Use of prohibited treatment as per Table 5-2. In case of initiation of open-label ACEI during the double blind treatment period, study medication must be stopped for ≥ 36 hours prior to initiation of open-label ACEI. The open label ACEI must be stopped for ≥ 36 hours prior to re-initiation of study drug.

Study medication may be discontinued at the investigator's discretion if any of the following occurs:

- Any severe suspected drug related AE
- Depending on the serum potassium, blood pressure, or eGFR, patients may need to have their study drug dose or the dose of another concomitant medication reduced or discontinued, or, if appropriate, have potentially contributing agents adjusted. Please refer to Appendix 2, Appendix 3, and Appendix 4 for treatment guidelines for hyperkalemia, hypotension, or renal dysfunction, respectively.
- Any other protocol deviation that results in a significant risk to the patient's safety

In the case of study drug discontinuation, the patient should continue to complete all scheduled study visits and procedures. If the patient refuses, he/she should be contacted by telephone in place of protocol-specified visits unless the patient expressly refuses such contacts.

The investigator must also record it on the drug administration form of the eCRF.

Patients may voluntarily withdraw from the study for any reason at any time. They may be considered withdrawn if they state an intention to withdraw, fail to return for visits, or become lost to follow-up for any other reason.

If premature withdrawal occurs for any reason, the investigator must make every effort to determine the primary reason for a patient's premature withdrawal from the study and record this information.

The investigator should discontinue study treatment for a given patient and/or withdraw the patient from study if, on balance, he/she believes that continuation would be detrimental to the patient's well-being.

Patients who discontinue study drug before completing the study or who prematurely withdraw from the study for any reason, should be scheduled for a visit as soon as possible at which time all (safety) assessments listed for the final end of study visit (EOS) will be performed.

The investigator must also contact the IRT to register the patient's discontinuation from investigational treatment. For patients who are lost to follow-up (i.e. those patients whose status is unclear because they fail to appear for study visits without stating an intention to withdraw), the investigator should show "due diligence" by documenting in the source documents steps taken to contact the patient, e.g. dates of telephone calls, registered letters, etc.

Patients who are prematurely withdrawn from the study **will not be replaced** by an equal number of newly enrolled patients.

5.5.11 Emergency breaking of treatment assignment

Emergency treatment code breaks should only be undertaken when it is essential to treat the patient safely and efficaciously. Most often, investigational treatment discontinuation and knowledge of the possible treatment assignments are sufficient to treat a study patient who presents with an emergency condition. Emergency treatment code breaks are performed using the IRT. When the investigator contacts the system to break a treatment code for a patient, he/she must provide the requested patient identifying information and confirm the necessity to break the treatment code for the patient. The investigator will then receive details of the investigational drug treatment for the specified patient. The system will automatically inform the Novartis monitor for the site and the Clinical Trial Head (CTH) that the code has been broken.

It is the investigator's responsibility to ensure that there is a procedure in place to allow access to the IRT in case of emergency. The investigator will inform the patient how to contact his/her backup in cases of emergency when he/she is unavailable. The investigator will provide protocol number, investigational treatment name if available, patient number, and instructions for contacting the local Novartis CPO (or any entity to which it has delegated responsibility for emergency code breaks) to the patient in case an emergency treatment code break is required at a time when the investigator and backup are unavailable.

5.5.12 Study completion and post-study treatment

The study will be considered completed when the patient completes the EOS visit (Visit 7). Patients will be asked to return the remaining study drug. The study as a whole will be considered completed when the last visit of last subject occurred.

The investigator must provide follow-up medical care for all patients who are prematurely withdrawn from the study, or must refer them for appropriate ongoing care.

5.5.13 Early study termination

The study can be terminated at any time for any reason specified in the clinical trial study contract, by Novartis. Should this be necessary, the patient should be seen as soon as possible and treated for a prematurely withdrawn patient. The sponsor will be responsible for informing IRBs and/or ECs of the early termination of the trial.

6 Visit schedule and assessments

Table 6-1 lists all of the assessments and indicates with an "x" which assessments are performed at each visit.

Patients should be seen for all visits on the designated day with an allowed "visit window" of "+/-3" days.

Patients who discontinue study drug before completing the study or who prematurely withdraw from the study for any reason, should be scheduled for a visit as soon as possible at which time all (safety) assessments, listed for the final EOS visit will be performed.

These patients should return for the assessments indicated by three asterisks (***) in Table 6-1. If they refuse to return for these assessments or are unable to do so, every effort should be made to contact them or a knowledgeable informant by telephone. Documentation of attempts to contact the patient should be recorded in the patient's record.

At a minimum, patients will be contacted for safety evaluations during the 30 days following the last study visit or following the last administration of study treatment if there are post-treatment follow-up visits (whichever is later), including a final contact at the 30-day point. Documentation of attempts to contact the patient should be recorded in the source documentation.

All data obtained from the assessments listed in Table 6-1 and described in detail in the subsections below must be supported in the patient's source documentation (e.g., medical charts or patient notes). Table 6-1 indicates which data remain in source documents only (S), or may be entered directly into the database (D; i.e., these data are considered source documentation and do not require separate source documentation), or are entered into the database from separate source documents (DS). Assessments that generate data for database entry and are recorded on eCRFs are listed using the eCRF name.

If one visit is postponed or brought forward, it should not result in the next visit being postponed or brought forward (except Visit 2 must be repeated for ergospirometry). The next visit, if at all possible and with the latter mentioned exceptions, should adhere to the original time schedule.

Patients will also be instructed to take study drug, as usual, on the morning of their site visits, with or without food. If a patient did not take his/her study drug on the morning of his/her scheduled visit, the study visit could nevertheless be conducted.

Table 6-1 Assessment schedule

Phase	D/S*	Screening		Double blind treatment**				
		1	2**	3**	4**	5**	6**	7/EOS***
Visit		D-16 to -12	D-9	D1	D14	D28	D42	D84
Days(D)/ Weeks (W)		W-2			W2	W4	W6	W12
Screening log	DS	x						
Informed consent form	DS	x						
Inclusion/Exclusion criteria	DS	x	x	x				
Demography	DS	x						
Medical history (including alcohol and smoking history)	DS	x						
Heart Failure History	DS	x						
Cardiovascular disease History	DS	x						
NYHA Classification (HF signs and symptoms)	DS	x	x	x	x	x	x	x***
Heart Failure and CV Medications	DS	x	x	x	x	x	x	x***
Concomitant Medications	DS	x	x	x	x	x	x	x***
Randomization	DS			x				
Physical Exam ¹	S	x	x	x	x	x	x	x***
Height (H) / Weight (W)	DS	H / W	W	W	W	W	W	W***
Vital signs	DS	x	x	x	x	x	x	x***
Waist/hip circumference	DS		x					x***
Echocardiography ²	DS	x						
Serum Pregnancy tests ³	DS	x						x***
Urine Pregnancy tests ³	DS		x					x***
AEs / SAEs	DS	x	x	x	x	x	x	x***
Complete laboratory assessments	DS	x	x					x***
Abbreviated chemistry panel ⁴	DS			x ⁹	x ⁹	x	x	

Phase	D/S*	Screening		Double blind treatment**				
		1	2**	3**	4**	5**	6**	7/EOS***
Visit	D/S*	1	2**	3**	4**	5**	6**	7/EOS***
Days(D)/ Weeks (W)		D-16 to -12 W-2	D-9	D1	D14 W2	D28 W4	D42 W6	D84 W12
12-lead ECG evaluation	S	x ⁵						
Ergospirometry	DS		x				x	x
Borg Scale documentation	DS		x				x	x
Double blind medication dispense	DS			x	x	x	x	
Contact IRT	S	x		x	x	x	x	x
Drug accountability	S			x	x	x	x	x
Treatment completion form	DS							x****
Study completion form	DS							x***

* DS: assessment to be documented in the clinical database, S: assessment to be recorded in the source data

** Visits marked with ** can be followed by unscheduled visits that may be performed at the investigator's discretion due to chemistry panel evaluation or up-titration.

*** Patients who prematurely discontinue study treatment should also return for the end of study (EOS) to collect at least safety assessments indicated by three asterisks (***).

**** To be documented at Visit 7 or at the time of premature discontinuation

1 Complete physical examination required at Visits 1, 2 and 7 (end-of-study visit). Short physical exam is sufficient at Visit 3 -6.

2 Qualifying LVEF measurements/documentation of structural heart disease will be based on obtained measurements (e.g. echocardiograms (echo)) performed ≤ 6 months prior to Visit 1. If an assessment performed ≤6 months prior to Visit 1 is not available, an echo must be performed during the screening epoch.

3 Women of childbearing potential only. At Visit 1 and 7 and in case of a positive urine pregnancy result, a confirmatory serum pregnancy test has to be performed at the central laboratory. A urine pregnancy test will be performed locally at Visit 2 and 7 and every time this is clinically indicated or a contraception gap has been reported.

4 Abbreviated chemistry panel including potassium, BUN, and serum creatinine will be measured at interim visits at the central laboratory.

5 Screening ECG performed within the 6 months before Visit 1 is accepted.

Phase		Screening		Double blind treatment**				
Visit	D/S*	1	2**	3**	4**	5**	6**	7/EOS***
Days(D)/ Weeks (W)		D-16 to -12 W-2	D-9	D1	D14 W2	D28 W4	D42 W6	D84 W12

9 At Visit 3 and 4, patients should come to the site 3 to 4 days prior to the scheduled visit date for blood draw only so that results from central laboratory are available and enable a competent decision on randomization or up-titration at the respective visits.

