Investigational drug	The drug whose properties are being tested in the study; this definition is consistent with US CFR 21 Section 312.3 and is synonymous with "investigational new drug" or "investigational medicinal product."
Investigational treatment	All investigational drug(s) whose properties are being tested in the study as well as their associated treatment controls. This includes any placebos, any active controls, as well as approved drugs used outside of their indication/approved dosage or tested in a fixed combination. Investigational treatment generally does not include other treatments administered as concomitant background therapy required or allowed by the protocol when used within approved indication/dosage
Medication number	A unique identifier on the label of each investigational/study drug package in studies that dispense medication using an IRT system
Subject Number	A number assigned to each patient who enrolls into the study
Part	A subdivision of a single protocol into major design components. These parts often are independent of each other and have different populations or objectives. For example, a single dose design, a multiple dose design that are combined into one protocol, or the same design with different patient populations in each part.
Period	A subdivision of a cross-over study
Premature patient withdrawal	Point/time when the patient exits from the study prior to the planned completion of all investigational/study treatment administration and all assessments (including follow-up)
Randomization number	A unique identifier assigned to each randomized patient, corresponding to a specific treatment arm assignment
Stop study participation	Point/time at which the patient came in for a final evaluation visit or when study/investigational treatment was discontinued whichever is later
Study drug/ treatment	Any single drug or combination of drugs administered to the patient as part of the required study procedures; includes investigational drug (s), active drug run-ins or background therapy
Study/investigational treatment discontinuation	Point/time when patient permanently stops taking study/investigational treatment for any reason; may or may not also be the point/time of premature patient withdrawal
Variable	Information used in the data analysis; derived directly or indirectly from data collected using specified assessments at specified time points

Protocol synopsis

Protocol number	CLCZ696BDE01

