5.5.5 Permitted dose adjustments and interruptions of study treatment

Every attempt should be made to maintain patients on the target study drug dose level for as long a duration as possible throughout the trial. If, however, in the opinion of the investigator, the patient does not tolerate the target dose of study drug, the investigator should consider whether non-disease-modifying medication (e.g., CCBs, diuretics, nitrates, α -blockers) can be reduced to rectify the situation, before considering to reduce the dose of the study drug to the next lower dose level.

Also, the investigator may adjust doses of disease-modifying medications if it is believed that they are the most likely cause of the adverse effect. If adjustment/elimination of concomitant medications is not possible or does not alleviate the side effects of concern, the investigator may down-titrate the dose of the study drug to the next lower level, up to complete withdrawal of the investigational treatment if necessary. The patient should be re-challenged with the higher dose when the investigator feels it is appropriate to do so per the directions provided below in this section. If needed, the study drug may be stopped completely, but the patient should continue to attend the study visits and be followed until the completion of the study. Ultimately,

the goal is to keep the patient on the highest study drug dose possible for as long as possible and to follow the patient in the study as long as possible.

Study drug dose level adjustments should mainly be based on overall safety and tolerability with special focus on a) hyperkalemia; b) symptomatic hypotension; and c) clinically significant decrease in eGFR/increase in serum creatinine (see Appendix 1, Appendix 2, Appendix 3, and Appendix 4 for treatment guidelines for hyperkalemia, management of BP, and renal dysfunction, respectively).

For patients who are unable to tolerate the protocol-specified dosing scheme, dose adjustments and interruptions of study treatment are permitted in order to keep the patient on study drug. The following guidelines should be followed:

Adjustment of study drug dose level

If despite adjustment of concomitant medications per the guidance provided above the situation is not rectified, the investigator may consider adjusting the study medication according the following instructions.

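### After study drug is stopped, section 5.5.10 keeps patients on every scheduled procedure, but section 6 sends them to a marked list that omits the exercise test

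*Protocol*

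**What the plan says.** Several places in the protocol address a patient who stops study drug but has not left the study.

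- **Glossary.** Stopping treatment and leaving the study are separate events. The point at which treatment is stopped "may or may not also be the point/time of premature patient withdrawal".
- **Section 5.5.5.** If drug is stopped completely, "the patient should continue to attend the study visits and be followed until the completion of the study". Procedures are not named.
- **Section 5.5.10, first rule.** After study drug discontinuation "the patient should continue to complete all scheduled study visits and procedures".
- **Section 5.5.10, later paragraph, and section 6.** One rule covers both groups: "Patients who discontinue study drug before completing the study or who prematurely withdraw from the study for any reason" are to have a prompt visit for the end-of-study assessments, with the word safety in brackets.
- **Section 6, next paragraph.** "These patients should return for the assessments indicated by three asterisks (*) in Table 6-1". (The mark in the protocol is three asterisks.)
- **Table 6-1, Visit 7 column.** The rows for Ergospirometry and "Borg Scale documentation" carry a plain x. The row "Study completion form" carries the three asterisks.
- **Footnote to the three asterisks.** Patients who stop treatment early are also to come back for the end-of-study visit, with the marked safety items as a minimum.

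On analysis, the full analysis set (FAS) is every randomized patient with at least one dose (Protocol 9.1). Missing VO2peak is filled by LOCF (Protocol 9.4.3, SAP 2.5.3). The other secondary efficacy variables are not imputed (SAP 2.7.3).

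**The concern.** The primary variable comes only from CPET, which is scheduled at Visits 2, 6 and 7. Whether a patient off drug still has the Visit 7 test decides whether the month-3 value is observed or filled in.

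The two rules start from different obligations. Under the first rule in 5.5.10 the patient owes the whole schedule. Under section 6 the patient owes one early visit with a marked subset that lacks CPET and contains the form that records the end of study participation. The telephone fallbacks differ in the same way: in 5.5.10 a call stands in for the protocol visits, in section 6 for the marked assessments.

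Sites could therefore collect different data on the same kind of patient. The values at risk belong to patients who stop drug, so the loss could not be assumed to be random.

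**Working it through.** The plan states no figure on this point, so the check is a reading of Table 6-1 against the text, followed by the analysis consequence.

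1. **Count of the visible Visit 7 entries.**
   - Three asterisks (12): NYHA class, HF and CV medications, concomitant medications, physical exam, weight, vital signs, waist/hip, serum pregnancy test, urine pregnancy test, AEs/SAEs, complete laboratory, Study completion form.
   - Four asterisks (1): Treatment completion form, due at Visit 7 or when treatment stops early.
   - Plain x (4): Ergospirometry, Borg, Contact IRT, Drug accountability.
   - 12 + 1 + 4 = 17.

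2. **What each rule requires of a patient who stops drug before Visit 6.**
   - 5.5.10, first rule: CPET at Visit 6 and at Visit 7.
   - Section 6, read literally: an early visit with the 12 marked items and no CPET.

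3. **What each rule requires of a patient who stops between Visits 6 and 7.**
   - 5.5.10, first rule: CPET at Visit 7.
   - Section 6, read literally: no further CPET.

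4. **Consequence if section 6 is followed literally and the patient is closed out.**
   - The patient stays in the FAS.
   - Stopped after Visit 6: the month-3 VO2peak is the week-6 value.
   - Stopped before Visit 6: the only earlier value is baseline. If baseline counts as an observed value, the change is baseline minus baseline = 0 at week 6 and at month 3. Neither document says whether baseline may be carried forward.
   - VE/VCO2 slope, watts at the ventilatory threshold and Borg are missing at the visits not performed.

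5. **What the plan has to detect this.**
   - Multiple imputation may be considered if more than 15% of data are missing or the arms are strongly imbalanced (Protocol 9.4.4, SAP 2.5.4). The denominator is not defined. If it is the 200 planned patients, 0.15 × 200 = 30, so the rate trigger needs more than 30 missing values.
   - SAP 2.11 summarizes change in adjusted VO2peak at Visits 6 and 7 by arm, limited to patients with both baseline and post-baseline values. It is descriptive and has no test.
   - SAP 2.3.1 tabulates study discontinuation and its reasons by arm.

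No effect on the estimate follows from these inputs. That would need the rate of stopping drug in each arm and the VO2peak such patients would have shown if tested, and the documents give neither.

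**The case against.** A reader might infer that the protocol tells sites to drop CPET, or to end follow-up, once drug is stopped. The documents do not support that, and the case against it is strong.

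- The first rule in 5.5.10 is explicit, and 5.5.5 is consistent with it.
- The footnote to the three asterisks frames the marked items as a minimum.
- The glossary dates the end of study participation by the later of the final evaluation visit and the stop of treatment.
- Section 5.5.12 ties completion to the end-of-study visit and identifies it as Visit 7, which Table 6-1 places at day 84. An early safety visit is not plainly that visit.
- A plain x does not mean an item lapses when drug stops. Contact IRT has a plain x at Visit 7, yet 5.5.10 requires IRT contact to register a discontinuation. Likewise, 5.5.3.1 asks for unused drug back at that time.
- The four-asterisk form already gives end of treatment its own record.
- Section 6 says that moving one visit should not move the next.

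All of this stands, and it makes the added-minimum reading the better one. It does not remove the conflict. Section 6 carries no such qualifier, names both groups in one sentence, and does not say that the early visit is additional to Visits 6 and 7. The Study completion form among the marked items points the other way.

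Two further inferences also go too far. Optional multiple imputation is not the only look at missing data, given SAP 2.11. Nor is this an argument against LOCF as such: the sponsor chose it with a stated reason, and it applies only where a value is missing.

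**Conclusion.** The concern holds as an inconsistency in the current protocol text with a possible, unquantified effect on the primary endpoint. The better reading keeps CPET at Visits 6 and 7 for patients off drug who remain in the study, but a site that follows section 6 as written could close such a patient out without it. The month-3 VO2peak would then be an LOCF value, and the secondary CPET endpoints would be missing at that visit.

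Size and direction cannot be derived. A reader might infer bias towards one arm or a loss of power of some stated amount; neither follows from the documents.

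The conclusion rests on the visible rows of Table 6-1 and on the protocol text alone. The separate CPET manual was not available and might settle the matter for sites. The point is worth correcting because the remedy is small and the endpoint at risk is the primary one.

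**What to change.** Reconcile the later paragraph of 5.5.10, section 6, Table 6-1 and its footnote with the first rule in 5.5.10:

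1. Separate patients who stop drug from patients who leave the study, as the glossary does.
2. State that for patients who stop drug and stay in the study, the early safety visit is additional to Visits 6 and 7 and does not replace them.
3. Add a note under Table 6-1 that Ergospirometry and Borg remain due at those visits for patients still in the study.
4. Tie the Study completion form to completing or leaving the study.
5. For patients already past Visit 7, report by arm how many month-3 VO2peak values after stopping drug are observed and how many are LOCF.

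The cost is amendment wording, one table note and one count by arm. No test is added beyond those that 5.5.10 already requires, and nothing changes about when study drug is stopped.

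There are limits. Some patients off drug will decline the test. Observed off-drug values may show a smaller difference between arms. The wording helps only patients not yet past Visit 7, and SAP section 4 already records an unblinding at a site, so the trial was under way when the SAP was written.
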